## 1.0 Protocol Summary

Title	A Pilot Study Evaluating the Feasibility and Usability of ToeFX Light Therapy Device for Mild to Moderate Distal Subungual Onychomycosis (DSO) of the Toenail
Short Title	ToeFX light therapy pilot
Methodology	Open label, prospective, multi-site, multi-investigator
Study Sites	
Hamilton Foot Clinic [name]
 
Bruyere Foot Specialists [name]
 
Wilson Foot Clinic [name]

Number of Study Subjects	100 subjects
Diagnosis and Main Inclusion Criteria	
Healthy males or females who meet the following criteria:
 
 
• are between 18-75 years of age.
 
• have a clinical diagnosis of mild to moderate DSO in the nail of at least one great toe, with 20% to 50% clinical involvement of the target toenail, without dermatophytomas or lunula (matrix) involvement, without lunular or proximal involvement.
 
• exhibit positive mycology results (ie, KOH test and culture of a dermatophyte) from the target great toenail, confirming common dermatophytes such as T. rubrum.
 
• are willing to abstain from any other treatment for onychomycosis for the duration of the pilot study.
 

Study Product and Planned Use	The ToeFX Light Therapy system is intended as a safe, effective and non-invasive treatment for nail fungus.

	This device will be used in accordance with the attached protocol. This study will be an open-label, prospective pilot study. The subjects will be 100 patients with mild to moderate onychomycosis. The purpose of the study is to establish the efficacy of the ToeFX device, which has shown compelling results in in vitro and ex vivo (cadaver) studies but has not been tested in patients.
Primary Endpoint	Technical Success: We will monitor (a) whether subjects attain 3 mm or more of clear nail growth post-treatment (b) whether subjects show mycological cure of their infection, as verified by culturing.
Secondary Endpoints	
 
• Usability and form factor reported by clinicians
 
• Satisfaction with the treatment reported by patients
 

## 2.0 Background: Clinical Need

According to a report published by the NCBI on January 14, 2015 (“Nail fungus: Overview”; Link: <https://www.ncbi.nlm.nih.gov/books/NBK279547/>), some 3 to 12% of the population is affected by toenail fungus, with older populations more likely to be affected. Indeed, fungal infection of nails (onychomycosis) is among the most prevalent infectious diseases in humans. According to a communication released by the Ontario College of Physicians and Surgeons in September 2019, the cure rate for topical treatments is only 6-23% after 1 year. Even after 1 year of treatment, topical treatments have limited efficacy. Moreover, onychomycosis is cosmetically distressing.

Beyond efficacy issues, treatment options for onychomycosis come with certain risks. A three-to-six-month regimen of oral antifungals comes with hepatotoxicity risk and a host of drug interaction possibilities. Most notably, the azole antifungals inhibit the most prevalent and critical hepatic enzyme (CYP3A4) in drug metabolism. Despite these interaction risks, oral therapy is more effective and takes up to 75% less time to complete than topical therapy. Cure rates for oral therapy fall between 45% to 70%, and total remission occurs for 35% to 80% of patients. (Source: *Onychomycosis Treatment: Are Topical Therapies Worthwhile?* Article published in July 2016 in *Contemporary Clinic* by Daniel Holland, Pharm D. Link: <https://contemporaryclinic.pharmacytimes.com/acute-care/onychomycosis-treatment-are-topical-therapies-worthwhile>)

## 2.1 Device Overview (LED light source)

The core component of the device is an LED light source emitting at two wavelength ranges. These wavelengths are red light at 630-680 nm (primary wavelength) and blue light at 450-470 nm (ancillary wavelength). The light source transfers energy to the infected region of the nails to break down fungus cells.

The light source operates with an accessory photosensitizer formulation based on the well-known aniline dye “methylene blue”. Methylene blue (MB) has been approved by Health Canada for several other indications, although not for the specific treatment of onychomycosis. In the ToeFX Light Therapy device, MB acts as a photosensitizer, mediating the transfer of energy from the red LED light source to the fungus. The MB concentration is 0.5%.

The mode of action is as follows: upon application of light, the photosensitizer molecule absorbs energy to form a short-lived excited state. The excited-state molecule rapidly transfers energy to surrounding oxygen to produce reactive oxygen species (ROS), which selectively disrupt the fungal cells. These ROS are short-lived and the reaction ceases immediately upon deactivation of the light.

The light device and photosensitizer formulation are used in conjunction. The formulation is painted onto the surface of the affected nail and allowed to penetrate into the nail bed for 10 to 15 minutes. Red light at an intensity of 200 mW/cm^2 is subsequently applied to the same area for 4 to 6 minutes. The nail may also be exposed to blue light at an intensity of 200 mW/cm^2. The blue light has no effect on the photosensitizer and is of secondary importance; however, several research groups have confirmed that exposure to mild blue light can have anti-inflammatory effects (Refer to Section 6.02, “Previous Studies”).

The treatment is administered 12 times over the course of 1 year. The light device has an expected lifetime of several thousand hours and is designed to dissipate ambient heat.

## 2.2 Procedural workflow

A foot care clinician applies a photosensitizer topically to infected toenails; the toenails are then exposed to the ToeFX light source for about 15 minutes. The patient visits the clinic to repeat the process at intervals of two weeks.

### Intended Users

User	Qualifications	Role & Location during ToeFX treatment	Interaction with ToeFX system
Chiropodist	
 
- Doctor of Chiropody
 
- Training in diagnosis and treatment of onychomycosis
 
	
 
- Assess severity of nail fungus and administer or supervise administration of treatment
 
	
 
- Deploys ToeFX system by administration of topical formulation
 
- Positions ToeFX light source over the infected area
 
- Removes the ToeFX light source at the treatment's end point.
 

Podiatrist	
 
- Doctor of Podiatry
 
- Training in diagnosis and treatment of onychomycosis
 
	
 
- Assess severity of nail fungus and administer or supervise administration of treatment
 
	
 
- Deploys ToeFX system by administration of topical formulation
 
- Positions ToeFX light source over the infected area
 
- Removes the ToeFX light source at the treatment's end point.
 

Physician assistant	
 
- Bachelor of Health Sciences (Physician Assistant specialization)
 
- Training supporting foot care clinicians
 
	
 
- Assist with administration of ToeFX treatment
 
- Collection of data, taking photographs of affected area
 
	
 
- May position light source over affected area and/or remove light source upon conclusion of the treatment.
 

## Operating Environment

The ToeFX system is intended for use in any room in which standard foot care treatments are routinely administered.

## 3.0 Study Objectives

This study will be an open-label, prospective pilot study. The subjects will be 100 patients who suffer from DSO. The efficacy of photodynamic therapy for treatment of onychomycosis has been demonstrated in the literature. The purpose of the study is to establish the efficacy of the specific ToeFX device, which has shown compelling results in *in vitro* and *ex vivo* (cadaver) studies but has not been tested in patients. Specifically, we wish to:

1. Determine the safety and efficacy of ToeFX photodynamic therapy in the treatment of distal subungual onychomycosis of the toenail.
2. Determine the number of treatments required to clear the nail and to cure the fungus.
3. Finalize the treatment protocol, device design and user interface.
4. Test re-infection or recurrence of fungus post-treatment.

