### 3.2 Study Design

Study Type:	Interventional (clinical trial)
Actual Enrollment:	100 participants
Masking:	None (Open Label)
Primary Purpose:	Treatment
Study Start Date:	Immediately upon approval by Health Canada

Arm	Intervention/treatment
Arm 1 Red light only	Core technology. Formulation and red light only. Apply photosensitizer; allow to penetrate for 15 minutes; apply red light for 15 minutes.
Arm 2 Red and blue light	Apply photosensitizer; place foot under blue light and allow to penetrate for 15 minutes. Apply red light for 15 minutes.

Arm 1 will test the core technology of the ToeFX system; this study reproduces protocols described in the literature (see ‘Previous Studies’ in Section 6.02). Arm 2 pairs the core technology with application of blue light. After application of the formulation, the nail is exposed to blue light at a wavelength of 450-470 nm and an intensity of 200 mW/cm^2. The blue light has no effect on the photosensitizer; however, several research groups have confirmed that exposure to mild blue light can have anti-inflammatory effects that would improve patient

outcomes (see ‘Previous Studies’ in Section 6.02). We will assess whether inclusion of blue light in the protocol affects the clinical outcome.

Debridement should be done prior to each treatment. Debridement should not be carried out more proximally than the most proximal margin of the dystrophic nail, as this can interfere with assessment of clear nail area attributable to the device intervention. Clinician should debride the nail and apply the photosensitizer formula and let it penetrate for 15 minutes, then if applicable apply the blue light (450-470 nm). Apply the red light (640 nm) for 15 minutes. The treatment is administered 12 times over the course of 1 year.

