### **3.4 Outcome Measures**

Clear nail: The specifications for clear nail are described below. The 95% one-sided confidence interval (i.e., lower bound only) around the observed response rate as described below should be  $\geq 50\%$ .

We will monitor whether subjects attain 3 mm or more of clear nail growth post-treatment. We will verify by taking a photograph prior to every treatment to assess the change in millimeters (mm) of clear nail bed. Millimeters (mm) of clear nail from the base of the toenail will be determined from digital photographs of the toenail and verified via software. The change in mm of clear nail bed will be calculated as the difference in mm of clear nail bed from baseline measurement to the measurement at the end of the procedure administration phase.

An increase in mm of clear nail between the two measurement points indicates that the toenail has improved and is positive for study success. A decrease in mm of clear nail between the two measurement points indicates that the toenail has worsened and is negative for study success.

Individual toenail success criterion is defined as 3 millimeter (mm) or more of clear nail growth as evaluated relative to baseline.

Length of the unaffected part of the target nail is measured in millimeters along the midpoint from the nail fold to the proximal border of the affected part (lowest point affected) along the midpoint of the target nail. Change from Baseline is: (Baseline value subtracted from 6-month treatment value). P-value shall be based on analysis of variance (ANOVA) with treatment and pooled center. Statistics will be provided for the adjusted least square mean.

To ensure adequate photographic quality and to maximize our ability to compare photographs across timepoints and across subjects, a standardized photography protocol will be put in place. Photographs shall be of high quality and high resolution. An internal scale (e.g. ruler) will be included in all images to allow objective measurement of millimeters of clear nail regardless of magnification of the image.

**Mycology:** Among toenails which are deemed responders based on the “clear nail” criteria, we will also assess for negative mycology (negative stain with concurrent negative culture, or two negative cultures from the same nail).

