**Follow-up:** The goal of treatments for onychomycosis is elimination of the fungal organism and full clearance of the nail. Follow-up for this indication should be based on the anticipated time for complete nail regrowth, which is approximately 6 months. Longer follow-up times will be helpful for assessing recurrence rates. To control for loss of subjects who do not exhibit the desired visual outcome, subjects who drop out or are lost to follow-up will be considered as treatment failures for this indication.

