### **3.6 Data Analysis**

- Descriptive statistical analysis to analyze degree of response (e.g., complete response or clearing, >75% clear, 50-75% clear).
- Increase in clear nail at each timepoint of evaluation after the last treatment
- Increase in clear nail as a function of the number of treatments

To evaluate the overall response rates, we plan to ensure that the study report be presented in a tiered fashion, citing the success rate for the subjects exhibiting mycological cure concurrent with clear nail, with separate presentation of the data for subjects exhibiting mycological cure with residual nail dystrophy.

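### Objective 2 asks how many treatments are required, but with one fixed 12-treatment course the count cannot be separated from elapsed nail-growth time

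*Combined protocol and SAP*

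**What the plan says.** Section 3.0 gives objective 2 as to "Determine the number of treatments required to clear the nail and to cure the fungus". The only analysis by treatment count is the third bullet of section 3.6: "Increase in clear nail as a function of the number of treatments". It names no model and no comparator, and it concerns the nail, not mycology.

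On the course, section 3.2 says "The treatment is administered 12 times over the course of 1 year", and section 2.1 says the same. Section 2.2 says "The patient visits the clinic to repeat the process at intervals of two weeks". The arms in section 3.2 differ only in blue light: "We will assess whether inclusion of blue light in the protocol affects the clinical outcome". No section assigns a different number of treatments to anyone or ends the course on clearance.

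On measurement, section 3.4 says "We will verify by taking a photograph prior to every treatment to assess the change in millimeters (mm) of clear nail bed", and "Individual toenail success criterion is defined as 3 millimeter (mm) or more of clear nail growth as evaluated relative to baseline". Its follow-up paragraph says "Follow-up for this indication should be based on the anticipated time for complete nail regrowth, which is approximately 6 months", and counts subjects who drop out or are lost as failures.

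On mycology, section 3.5 requires a positive KOH test and culture at entry. Later mycology appears in three places: section 1.0 (culture-verified cure in subjects, as part of the primary endpoint), section 3.4 (negative mycology among clear-nail responders) and section 3.6 (separate reporting of cure with residual dystrophy). None of the three gives a sampling visit.

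**The concern.** A number of treatments required is a dose-response quantity. To learn it, a trial needs either subjects who receive different numbers of treatments or a marker that shows promptly when enough has been given. Here everyone is on the same course. The visible marker, clear nail, trails any effect on the fungus because the affected plate has to grow out. Shorter courses from dropout do not help: once they are coded as failures, fewer treatments look ineffective by definition.

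If the curve in section 3.6 were read as the answer to objective 2, the reported number would reflect growth rate, visit spacing and baseline extent of disease. Objective 3 is to finalize the treatment protocol, so such a number could be carried forward.

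**Working it through.** **1. The schedule as stated.** Twelve visits two weeks apart end at week 11 × 2 = 22. Twelve over a 52-week year means one every 52/12 = 4.3 weeks, or 52/11 = 4.7 weeks if the first and last fall at the two ends. Sections 2.2 and 2.1/3.2 therefore do not agree. The steps below use both.

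**2. Count against time.** With fixed visits, treatment *j* falls at (*j* − 1) × interval, so the correlation between count and time is exactly 1 on either schedule. The documents state no visit window. With assumed windows of ±3 or ±7 days (simulated, 100 subjects × 12 visits), the correlation is 0.997 to 0.9999. The variance inflation, 1/(1 − r²), is about 160 to 3,800.

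**3. Two opposite explanations, one curve.** The documents give no growth rate; assume 1.5 mm a month, and visits every 52/12 weeks (one month).
- A: the first treatment suffices and the nail then grows out. Clear growth at the *j*-th later visit = 1.5 × *j*.
- B: each treatment adds one interval of growth. Clear growth after *j* treatments = 1.5 × *j*.

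Both give 0, 1.5, 3.0, … 16.5 mm over the 12 pre-treatment photographs. More subjects would not tell them apart.

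**4. Hypothetical worst case for clearance.** Inputs: full regrowth in about 6 months, taken as 26 weeks (section 3.4); involvement of 20% to 50% (section 3.5). Assumptions: uniform growth, affected length share equal to the involvement, and a first treatment that suffices. Grow-out time = 26 × 0.20 = 5.2 weeks to 26 × 0.50 = 13 weeks. The first pre-treatment photograph at or after that point is:

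| Spacing | 20% involved | 50% involved |
|---|---|---|
| 2 weeks | week 6, 3 treatments received | week 14, 7 received |
| 52/12 weeks | week 8.7, 2 received | week 13, 3 received |
| 52/11 weeks | week 9.5, 2 received | week 14.2, 3 received |

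The true number in this example is 1.

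**5. If more are truly needed.** Suppose *k* treatments are needed and clear growth starts only at the *k*-th. The counts become *k* + 2 to *k* + 6 at two-week spacing, and *k* + 1 to *k* + 2 at 12 per year. For *k* = 4 these are 6 to 10 (ratio 1.5 to 2.5) and 5 to 6 (ratio 1.25 to 1.5). The excess stays but the ratio shrinks.

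**6. The plan's own 3 mm criterion.** Assume growth of 1.0 to 2.0 mm a month. Then 3 mm takes 3/2.0 = 1.5 months to 3/1.0 = 3 months, or 6.5 to 13 weeks at 52/12 weeks a month. From growth alone, the first photograph to show it follows 4 to 7 treatments at two-week spacing, and 2 to 3 at 12 per year.

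**7. Cure.** No sampling occasion is specified between screening and the undated outcome assessment, so the plan does not provide for observing the treatment number at cure.

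**The case against.** The best reply is that this is a pilot and the section 3.6 bullet is descriptive. Objective 2 is neither a primary nor a secondary endpoint, and no success criterion depends on it. Read as treatments received by the time of response under this schedule, it can be reported from the photographs. That stands, and the fix keeps it. It does not rescue the wording of section 3.0, which promises to determine a required number.

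Some stronger readings are tempting, and the documents do not support them:
- *Mycology is ruled out during the course, or limited to responders.* Section 3.4 speaks of responders, but sections 1.0 and 3.6 provide for cure in subjects more widely. What is missing is the timing.
- *The planned readout overstates the number 2- to 7-fold.* No section defines a readout as the first fully clear photograph, and none ties the section 3.6 bullet to objective 2. Those ratios also need a true number of 1 and an area share equal to a length share. Debridement before each treatment may also affect when a nail looks clear.
- *Objective 3 will rest on this number.* That is an inference; no section says so.

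One might also hope to rescue the objective with a count of treatments to first visible improvement. That would still be a count tied to time, and it would need a millimetre threshold that the plan does not give. Dated mycology samples would show the treatment number at the first negative result, but would add procedures and still would not separate count from time.

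**Conclusion.** The point holds in a limited form. Under a single planned course of 12, the number of treatments required to clear the nail cannot be identified, whichever schedule is followed and however many subjects are enrolled. For cure, no sampling visit during the course is specified, so that half of the objective has even less to rest on.

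This conclusion needs only the fixed course and the lag in nail growth; it does not depend on the assumed growth rates or visit windows. The 3 to 7 and 2 to 3 treatments in the clearance example are a worst case that shows the direction and possible size of the distortion. They do not estimate an error in a stated result. A reader might take the conflict between the schedules as evidence that the course is not fixed; on either reading count still tracks time, and if sites read it differently, spacing would be confounded with site. The primary endpoint is not affected.

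**What to change.** - **Section 3.0.** Reword objective 2 to: *describe the time course of clear-nail growth, and the number of treatments received and weeks elapsed when the 3 mm criterion is first met, under the 12-treatment schedule*. Remove cure of the fungus from this objective.
- **Section 3.6.** Report the third bullet by both treatment number and weeks since first treatment, by arm, and add: *No number of treatments required for clearance or cure will be inferred, because treatment count and elapsed time are not separable in this design.*
- **Sections 2.1, 2.2 and 3.2.** Reconcile the two-week interval with 12 treatments over a year, so that weeks and counts mean the same at every site.

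The changes to 3.0 and 3.6 are wording only and use photographs already planned. They need no extra subjects or procedures. The downside is that the sponsor gives up a claim about the number of treatments required.

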## 3.1 Overview of Study

### Definition of distal subungual onychomycosis (DSO)

This type of onychomycosis is the most common clinical presentation, in which the distal nail plate is separated from the nail bed. This infection presents as nails with normal surface texture and thickness but variable “bays” of white nail that extend from the distal nail tip proximally into

the area of the nail bed. This form has been the cornerstone of antifungal drug studies. Since it generally does not involve the nail matrix, it is more amenable to improvement in clinical appearance than some other forms. In this trial only mild to moderate DSO cases will be included using the Onychomycosis Severity Index (OSI). An OSI score is obtained by multiplying the score for the area of involvement (range, 0-5) by the score for the proximity of disease to the matrix (range, 1-5).

A clinician or delegate will:

- Take representative before and after photos of nail/s prior to treatment.
- Provide a description of the treatment protocol used, including any adjunctive interventions such as topical antifungal products or debridement.
- Record occurrences and frequency of any adverse events.
- Prepare a table summarizing the percent complete responders, partial responders (which may be further stratified), and non-responders.
- Ensure that fungal species are assessed.
- Ensure that clinical presentations of onychomycosis are assessed (e.g., DSO).

### 3.2 Study Design

Study Type:	Interventional (clinical trial)
Actual Enrollment:	100 participants
Masking:	None (Open Label)
Primary Purpose:	Treatment
Study Start Date:	Immediately upon approval by Health Canada

Arm	Intervention/treatment
Arm 1 Red light only	Core technology. Formulation and red light only. Apply photosensitizer; allow to penetrate for 15 minutes; apply red light for 15 minutes.
Arm 2 Red and blue light	Apply photosensitizer; place foot under blue light and allow to penetrate for 15 minutes. Apply red light for 15 minutes.

Arm 1 will test the core technology of the ToeFX system; this study reproduces protocols described in the literature (see ‘Previous Studies’ in Section 6.02). Arm 2 pairs the core technology with application of blue light. After application of the formulation, the nail is exposed to blue light at a wavelength of 450-470 nm and an intensity of 200 mW/cm^2. The blue light has no effect on the photosensitizer; however, several research groups have confirmed that exposure to mild blue light can have anti-inflammatory effects that would improve patient

outcomes (see ‘Previous Studies’ in Section 6.02). We will assess whether inclusion of blue light in the protocol affects the clinical outcome.

Debridement should be done prior to each treatment. Debridement should not be carried out more proximally than the most proximal margin of the dystrophic nail, as this can interfere with assessment of clear nail area attributable to the device intervention. Clinician should debride the nail and apply the photosensitizer formula and let it penetrate for 15 minutes, then if applicable apply the blue light (450-470 nm). Apply the red light (640 nm) for 15 minutes. The treatment is administered 12 times over the course of 1 year.

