## **4.0 Study Procedures**

### **4.1 Patient Recruitment and Screening**

Potential study subjects will be identified by the co-investigators or any sub-investigators. It is anticipated that surgical consults will be the primary source of study candidates. Clinicians will ask patients who present with onychomycosis if they are interested in participating in the research trial; those who are interested will be assessed by the clinician for their compatibility with the inclusion/exclusion criteria. Patients that meet all criteria will be asked to submit a nail sample for mycological culturing. This initial review of existing patient information may be performed prior to subject consent; however, no protocol-driven tests or procedures may be performed until after informed consent has been obtained. If the subject shows positive mycology, he/she will be contacted via phone within 2 weeks and asked to sign an informed consent form in person, where a clinician will be present to answer any questions. If the patient is satisfied and has no questions, the treatments may commence at the clinic during the same visit. Research participants will remain in the study for one year.

For the occasional non-English speaking study participant, an on-site translator will be provided at the clinic at the expense of the Sponsor. Informed consent will be treated as an ongoing

process throughout a study. For those who understand English but cannot read, talk, or write, the investigator will provide the necessary support to ensure the subject's ongoing comprehension of new information that may become available during the study.

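### The plan gives no rule for assigning subjects to the red or red-and-blue arm, so its assessment of blue light is open to confounding

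*Combined protocol and SAP*

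**What the plan says.** Section 3.2 (Study Design) sets out Arm 1, photosensitizer and red light, and Arm 2, of which it says: "Arm 2 pairs the core technology with application of blue light". It then states a between-arm aim: "We will assess whether inclusion of blue light in the protocol affects the clinical outcome". Section 3.4 (Outcome Measures) says of the change in millimetres of clear nail: "P-value shall be based on analysis of variance (ANOVA) with treatment and pooled center". With two arms defined, the natural reading of treatment in that model is arm.

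On assignment the plan is silent:

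- The methodology entry in section 1.0 reads "Open label, prospective, multi-site, multi-investigator" and does not mention randomisation.
- The design table in section 3.2 has entries for study type, enrolment, masking (none), purpose and start date, but none for allocation.
- The procedure paragraph in section 3.2 says "then if applicable apply the blue light (450-470 nm" without saying what makes blue light applicable.
- Section 4.1 (Patient Recruitment and Screening) goes from consent to treatment with no assignment step: "If the patient is satisfied and has no questions, the treatments may commence at the clinic during the same visit".
- Section 4.3 gives each consented subject a number, not an arm.

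**The concern.** A clinic could follow this protocol to the letter and still give blue light to patients picked by the clinician, or run one arm only. Section 3.2 supplies a motive for choosing, since it tells clinicians that blue light may improve outcomes. The eligibility range of 20% to 50% nail involvement (section 3.5) leaves some spread in severity on which to select. The planned ANOVA contains no baseline severity term.

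At stake is the trial's only concurrent comparison. Objective 3 in section 3.0 is to finalise the treatment protocol, and a difference between arms could feed that decision. If the difference reflects who was put in which arm, it says little about blue light, and allocation cannot be randomised after subjects have been enrolled and treated.

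**Working it through.** **1. The plan's own figure.** Section 3.3 says that 100 patients are adequate, given 15-18% complete cure in the published topical trial and 50-80% expected here. No alpha, power or formula is stated, so the 100 cannot be derived, but the claim of adequacy can be checked. Assume an exact binomial test of 50% against a fixed 18% at one-sided 0.025. The rule is 27 or more responses of 100, with actual alpha 0.017 and power above 99.99%. The claim holds, but it concerns the whole cohort against a historical rate and says nothing about Arm 1 against Arm 2.

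**2. What the center term can do.**

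- *Every clinic runs both arms.* Arm is compared within clinic, and average differences between clinics drop out. Selection of patients within a clinic stays in the estimate.
- *Each clinic uses one arm only.* Arm is then fixed by clinic, and a model containing both terms cannot estimate an arm effect. If clinics with different arms are pooled into one center level (no pooling rule is given), an estimate appears, but it contains the difference between those clinics.

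**3. How much selection could matter (illustration).** None of these inputs is in the documents; all are assumed: 50 per arm, two-sided 5% test, no blue-light effect, response 80% in milder nails and 50% in worse nails. If a share q of an arm's nails is milder, its response rate is

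p = 0.80 q + 0.50 (1 - q),

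so the false difference is 0.30 × (q2 - q1).

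The average rate is 0.65 in every row below. The null standard error is sqrt(0.65 × 0.35 × 2/50) = 0.0954, and the test rejects beyond 1.96 × 0.0954 = 0.187. The standard error of the observed difference is sqrt[p1(1 - p1)/50 + p2(1 - p2)/50].

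| Share milder, one arm / other | Response rates | False difference | False-positive rate |
|---|---|---|---|
| 50% / 50% | 65% / 65% | 0 | 5% |
| 40% / 60% | 62% / 68% | 6 points | 9.6% |
| 30% / 70% | 59% / 71% | 12 points | 24% |
| 20% / 80% | 56% / 74% | 18 points | 47% |

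For the 40/60 row, the standard error is sqrt[(0.2356 + 0.2176)/50] = 0.0952. The upper tail is at (0.06 - 0.187)/0.0952 = -1.33, giving 0.091. The lower tail is at (-0.06 - 0.187)/0.0952 = -2.59, giving 0.005. The total is 0.096.

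These are response proportions. The planned ANOVA is on millimetres, where the same mechanism gives a bias of (q2 - q1) times the prognostic gap in millimetres. The documents give neither that gap nor a standard deviation, so no figure is put on it.

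**4. The same imbalance under randomisation.** With half of nails milder and 50 per arm, the difference in shares has standard error sqrt(2 × 0.5 × 0.5/50) = 0.10. A gap of 20 points or more (two standard errors) occurs about 4.6% of the time, and 40 points or more (four standard errors) under 0.01%. The test keeps its 5% level because these chance imbalances are already counted in it.

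**5. Precision once randomised.** At 60% response and 50 per arm (assumed), the 95% half-width for the difference is 1.96 × sqrt(2 × 0.6 × 0.4/50) = 0.192, about ±19 points. At 80% power and two-sided 5%, the smallest detectable difference is about 24 to 27 points for red-only rates of 50% to 65%. Randomisation does not change these figures. They bear on how the result is labelled, and they are not evidence of bias.

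**The case against.** The strongest reply is that blue light is a side question. It is absent from the four objectives, the endpoints, the sample-size statement and the section 3.6 analysis list, and section 2.1 calls it of secondary importance. The success criterion in section 3.4 is a lower bound of at least 50% on a response rate, and the control in section 3.3 is a published trial. Neither contrasts the arms. All of this stands, and it limits the reach of the point. It does not remove the sentence in section 3.2 that promises the assessment, or the treatment term in the ANOVA.

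Three stronger readings are tempting, and the documents do not support them:

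- *That clinicians will choose the arm, so the comparison is confounded.* The plan leaves assignment open; it does not say that clinicians choose. Starting treatment at the consent visit is permitted rather than required, and section 4.2 lets any delegated staff member take consent.
- *That any clinic difference passes into the estimate.* The center term removes average clinic differences if each clinic runs both arms.
- *That a bias of a particular size is to be expected.* The documents give no blue-light effect, no prognostic gap and no split by severity. Eligibility restricted to mild to moderate disease narrows the room for selection.

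It is also fair to say that measurement has some protection: section 3.4 calls for standardised photographs with an internal scale and software verification. That guards against loose measurement but not against unequal groups.

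**Conclusion.** The point holds for the blue-light comparison only. Two arms, a stated between-arm aim and a treatment term in the ANOVA are present; an assignment rule is not. The comparison is open to confounding by selection within a clinic, and it is not separable from clinic if each clinic uses one arm. Under the assumptions of the illustration, false positives rise from 5% to about 10% with a 40/60 split of milder nails and to about 24% with a 30/70 split. These figures show the mechanism and do not predict what will happen.

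The one-sample 50% bound and the comparison with the published topical trial stand or fall on other grounds. The conclusion rests on the text from the Protocol Summary onward, and on reading treatment in section 3.4 as arm. It needs settling before enrolment, because allocation cannot be repaired afterwards.

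**What to change.** In section 3.2, state that subjects are randomised 1:1 to Arm 1 or Arm 2, stratified by clinic, with allocation concealed until consent and eligibility are complete. Permuted blocks within clinic, issued from a central list or sealed numbered envelopes, would do. Add the assignment step to section 4.1.

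In section 3.4, state that the arms are analysed as allocated with clinic as a factor, that the comparison is exploratory, and that the difference is reported with its 95% interval.

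The cost is a randomisation list and a paragraph of amendment text; the total stays at 100. The downside is practical: every clinic must be able to run both arm procedures.

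If the sponsor does not randomise, remove from section 3.2 the statement that the effect of blue light will be assessed, remove the between-arm p-value from section 3.4, and report the two arms descriptively. That costs nothing except the comparative claim.
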